4.4 Other Restrictions

5 Reporting of Adverse Events

5.1 Definitions

An AE is defined as any untoward medical occurrence in a patient or clinical trial subject administered a medicinal product and which does not necessarily have a causal relationship with this treatment. Adverse events would not include information recorded as complications at screening for preplanned procedures for which the underlying condition was known and no worsening occurred. An adverse drug reaction is any untoward and unintended response to an IMP related to any dose administered.

A suspected adverse reaction is any AE for which there is a reasonable possibility that the IMP caused the AE. For the purpose of Investigational New Drug safety reporting, "reasonable possibility" means there is evidence to suggest a causal relationship between the IMP and the AE. Suspected adverse reaction implies a lesser degree of certainty about causality.

An SAE includes any event that results in any of the following outcomes:

- Death
- Life-threatening; ie, the subject was, in the opinion of the investigator or subinvestigator, at immediate risk of death from the event as it occurred. It does not include an event that, had it occurred in a more severe form, might have caused death.
- Persistent or significant incapacity/disability or substantial disruption of the ability to conduct normal life functions.
- Requires inpatient hospitalization or prolongs hospitalization
 - Hospitalization itself should not be reported as an SAE; whenever possible the reason for the hospitalization should be reported.
 - Hospitalizations or prolonged hospitalizations for social admissions (ie, those required for reasons of convenience or other nonmedical need) are not considered SAEs.
- Congenital anomaly/birth defect.
- Other medically significant events that, based upon appropriate medical judgment, may jeopardize the subject and may require medical or surgical intervention to prevent one of the outcomes listed above, eg, allergic bronchospasm requiring intensive treatment in an emergency room or home, blood dyscrasias or convulsions

that do not result in hospitalization, or the development of drug dependency or drug abuse.

Nonserious AEs are all AEs that do not meet the criteria for a "serious" AE.

Immediately Reportable Event (IRE):

- Any SAE
- Any AE related to occupational exposure.
- Potential drug-induced liver injury (see Section 5.4 Potential Drug-induced Liver Injury).
- Pregnancies are also defined as IREs. Although normal pregnancy is not an AE, it will mandate IMP discontinuation and must be reported on an IRE form to the sponsor. Pregnancy will only be recorded in the AE section of the CRF if there is an abnormality or complication.

Clinical Laboratory Assessment Value Changes: It is the investigator's or subinvestigator's responsibility to review the results of all laboratory tests as they become available. This review will be documented by the investigator's or subinvestigator's dated signature on the laboratory report. For each abnormal laboratory test result, the investigator or subinvestigator needs to determine whether this is an abnormal (ie, clinically relevant) change from baseline for that individual subject. This determination, however, does not necessarily need to be made the first time an abnormal value is observed. The investigator or subinvestigator may repeat the laboratory test or request additional tests to verify the results of the original laboratory tests. If this laboratory value is considered medically relevant by the investigator or subinvestigator (subject is symptomatic, requiring corrective treatment or further evaluation), or if the laboratory value leads to discontinuation or meets the criteria for an SAE, this is considered an AE.

Severity: Adverse events will be graded on a 3-point scale. The intensity of an AE is defined as follows:

- 1 = Mild: Discomfort noticed, but no disruption to daily activity.
- **2** = **Moderate:** Discomfort sufficient to reduce or affect normal daily activity.
- **3** = **Severe:** Inability to work or perform normal daily activity.

IMP Causality: Assessment of causal relationship between an AE and the IMP:

- **Related**: There is a reasonable possibility of a temporal and causal relationship between the IMP and the AE.
- **Not related**: There is no temporal or reasonable relationship between the IMP and the AE.

5.2 Eliciting and Reporting Adverse Events

The investigator or subinvestigator will periodically assess subjects for the occurrence of AEs. To avoid bias in eliciting AEs, subjects should be asked the non-leading question: "How have you felt since your last visit?" All AEs (serious and nonserious) reported by the subject must be recorded in the source documents and CRFs provided by the sponsor. The event name, date and time of onset, date and time of recovery, seriousness, severity, causal relationship to IMP, actions taken regarding IMP administration, and outcome thereof will be recorded in the CRF. The period for AE and SAE collection is defined as the period from after a subject has signed the ICF to the date of trial completion.

Use medical terminology in AE reporting. Adverse events should be reported as a single unifying diagnosis whenever possible or, in the absence of a unifying diagnosis, as individual signs or symptoms. Exacerbation or disease progression should be reported as an AE only if there are unusual or severe clinical features that were not present, or experienced earlier, or not expected on the basis of the course of the condition.

Worsening of severity and seriousness of reported AEs must be reported as new AEs in the CRF.

In addition, the sponsor must be notified immediately by e-mail of any IREs according to the procedure outlined below, in Section 5.3 Immediately Reportable Events. Special attention should be paid to recording hospitalization and concomitant medications.

5.3 Immediately Reportable Events

The investigator, subinvestigator, or designee must report any and all IREs (see Section 5.1 Definitions) to the sponsor by e-mail (using the contact information on the title page of this protocol) immediately after either the investigator, subinvestigator, or designee becomes aware of the event. An IRE form must be sent by e-mail to the sponsor. Please note that the IRE form is NOT the AE section of the CRF. Due consideration must be given to the subject's privacy when an IRE form is sent by e-mail.

For subjects experiencing SAEs or IREs, such events should be followed until the events are resolved or clinically stabilized, or the subject is lost to follow-up. *Resolved* means

that the subject has returned to the baseline state of health, and *stabilized* means that the investigator or subinvestigator does not expect any further improvement or worsening of the subject's condition. It is expected that the investigator or subinvestigator will provide or arrange appropriate supportive care for the subject and will provide prompt updates on the subject's status to the sponsor.

5.4 Potential Drug-induced Liver Injury

For a subject who experiences an elevation in aspartate aminotransferase (AST) or alanine aminotransferase (ALT) that is ≥ 3 times the ULN, total bilirubin level should also be evaluated. If the total bilirubin is ≥ 2 times the ULN, complete the IRE form and so on with all values listed and also report as an AE in the CRF.

5.5 Pregnancy

Women of childbearing potential are defined as female subjects for whom menstruation has started and who are not documented as sterile (ie, have had a bilateral oophorectomy and/or hysterectomy or who have been postmenopausal for at least 12 months).

For WOCBP and for men who are sexually active, there must be a documented agreement that the subject and/or their partner will take effective measures (ie, double-barrier method) to prevent pregnancy during the course of the trial and for 30 days after the final administration of IMP. Unless the subject or their partner is sterile (ie, women who have had a bilateral oophorectomy and/or hysterectomy or who have been postmenopausal for at least 12 consecutive months; or men who have had a bilateral orchidectomy) or remains abstinent, 2 of the following precautions must be used: vasectomy, tubal ligation, vaginal diaphragm, IUD, oral contraceptives, or condom with spermicide. Any single method of birth control, including vasectomy and tubal ligation, may fail, leading to pregnancy. The contraceptive method will be documented at each trial visit.

Before enrolling WOCBP in this clinical trial, investigators or subinvestigators must review the below guidelines about trial participation with all WOCBP. The topics should generally include:

- General information
- Informed consent form
- Pregnancy prevention information
- Drug interactions with hormonal contraceptives
- Contraceptives in current use
- Guidelines for the follow-up of a reported pregnancy

Before trial enrollment, WOCBP must be advised of the importance of avoiding pregnancy during trial participation and the potential risk factors for an unintentional pregnancy. The subject must sign an informed consent form stating that the above-mentioned risk factors and the consequences were discussed with her.

All WOCBP must undergo a urine or serum pregnancy test (human chorionic gonadotropin [HCG] test) at screening. If a urine test is performed and is positive, the investigator or subinvestigator will follow up with a confirmatory serum test.

During the trial, all WOCBP should be instructed to contact the investigator or subinvestigator immediately if they suspect they might be pregnant (eg, missed or late menstrual cycle).

If a subject is suspected to be pregnant before the start of IMP administration, the IMP administration must be withheld until the results of pregnancy tests are available. If the pregnancy is confirmed, the subject must not receive the IMP and must not be enrolled in the trial. If pregnancy is suspected while the subject is taking IMP, the IMP must be withheld immediately (if reasonable, taking into consideration any potential withdrawal risks) until the result of the serum pregnancy test is known. If pregnancy is confirmed, the IMP will be permanently discontinued in an appropriate manner (eg, dose tapering if necessary for subject safety) and the subject will be withdrawn from the trial. (Exceptions to trial discontinuation may be considered for life-threatening conditions only after consultations with the PV department [see the cover page of this protocol for contact information].)

The investigator or subinvestigator must immediately notify the sponsor of any pregnancy associated with IMP exposure during the trial and for 30 days after the final administration of IMP, and record the event on the IRE form, and forward it to the sponsor. The sponsor will forward Pregnancy Surveillance Form(s) for monitoring the outcome of the pregnancy. The same applies to the pregnancy of a subject's partner.

Protocol-required procedures for trial discontinuation and follow-up must be performed on the subject unless contraindicated by pregnancy (eg, x-ray studies). Other appropriate pregnancy follow-up procedures should be considered, if indicated. In addition, the investigator or subinvestigator must report to the sponsor, on appropriate Pregnancy Surveillance Form(s), follow-up information regarding the course of the pregnancy, including perinatal and neonatal outcome. Infants will be followed for a minimum of 6 months from the date of birth.

5.6 Procedure for Breaking the Blind

Only in the event that a subject has a medical emergency and knowledge of the treatment assignment code is necessary for treatment, the investigator or subinvestigator may obtain the emergency key code for the subject in question through the IWRS, in accordance with the separately specified procedures. When emergency key code opening is performed, the sponsor will receive automatic notification from the IWRS via e-mail. If the emergency key code is opened, the PV department must be notified immediately (see the cover page of this protocol for contact information).

Documentation of emergency key code opening should be recorded in the subject's medical record with the date and time of opening and the names of the personnel involved. Once a subject's emergency key code is opened, IMP administration may not be reinitiated for that subject.

5.7 Follow-up of Adverse Events

5.7.1 Follow-up of Nonserious Adverse Events

Nonserious AEs that are identified at any time during the trial must be recorded in the AE section of the CRF, with the current status (ongoing or resolved/recovered) noted. All nonserious events (other than IREs) that are ongoing at the end of trial date (final day of observation) will be recorded as ongoing in the CRF. For any AE having been identified throughout the trial, during data analysis, additional relevant medical history information may be requested by the sponsor to further ascertain causality (including, but not limited to, information such as risk-related behavior, family history, and occupation). The follow-up information after the end of trial date (final day of observation) will be recorded in the subject's medical record.

5.7.2 Follow-up of Serious Adverse Events and Immediately Reportable Events

This trial requires that subjects be actively monitored for SAEs and IREs up to the end of trial date (final day of observation).

Serious AEs and IREs that are identified or ongoing at the end of trial date must be recorded in the AE section of the CRF. Between the end of trial date for the individual subject and the end of trial date for the last subject, if any new information regarding an SAE or IRE becomes available (eg, the event is resolved), this must be reported to the sponsor using the IRE form and so on, and the information must be recorded in the AE section of the CRF. The investigator or subinvestigator will follow SAEs and IREs, and will continue to report any significant information to the sponsor until the events are

resolved or stabilized, or the subject is lost to follow-up or has died, using the IRE form and so on.

5.7.3 Follow-up and Reporting of Serious Adverse Events and Immediately Reportable Events Occurring After the End of Trial Date (Final Day of Observation)

Any new SAEs or IREs reported to the investigator or subinvestigator, which occur after the end of trial date (final day of observation) and are determined by the investigator or subinvestigator to be associated with the use of the IMP, should be reported to the sponsor. This includes SAEs and IREs that are captured on follow-up telephone contact or at any other time point after the defined trial period. The investigator or subinvestigator will follow SAEs and IREs identified after the defined trial period and continue to report any significant follow-up information to the sponsor until the events are resolved or stabilized, or the subject is lost to follow-up or has died, using the IRE form and so on.

6 Statistical Analysis

The definitions of the datasets for analysis and the analysis methods for the specified endpoints are described below. The statistical analysis plan details are described in a separate Statistical Analysis Plan. The Statistical Analysis Plan will be finalized prior to data lock.

6.1 Determination of Sample Size

In Trial 331-12-283, which was performed outside Japan, the 2 mg fixed-dose group showed superiority over the placebo group in patients with aggression (patients with aggressive behavior at baseline), thus suggesting that it may also be the optimum dose for Japanese patients. Efficacy was not observed in the 1 mg fixed-dose group, but in Trial 331-12-284, the efficacy of a dose less than 2 mg was suggested by the results obtained in patients from the flexible-dose (0.5 to 2 mg) group, who had aggression.

In this trial, a power of detection $\ge 80\%$ will be achieved for comparison between the placebo group and the 1 mg group to allow evaluation of superiority over the placebo group if equivalent efficacy is demonstrated in the 1 and 2 mg groups. For comparison between the 2 mg group (possible optimum dose) and the placebo group, a more sufficient power of detection will be obtained by changing the randomization ratio. In this trial, it is assumed that the difference between the 2 mg group and the placebo group in the change in the CMAI total score from baseline to Week 10 is -5.35, and the standard deviation (calculated from the standard error of the difference between the 2 mg and placebo groups and the number of subjects at baseline) is 15.06 on the basis of the results

of Trial 331-12-283. By setting the number of subjects in the 2 mg group, 1 mg group, and placebo group as 148, 111, and 148, respectively (randomization ratio of 4:3:4), the power of detection is 86.1% for the comparison between the 2 mg group and the placebo group and is 80.5% for the comparison between the 1 mg group and the placebo group in a test with a significance level of 5% (two sided).

On the basis of the above considerations, the number of subjects will be set at 148 in the 2 mg group, 111 in the 1 mg group, and 148 in the placebo group (randomization ratio of 4:3:4).

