	group, a more sufficient power of detection will be obtained by
	changing the randomization ratio. In this trial, it is assumed that the
	difference between the 2 mg group and the placebo group in the
	change in the CMAI total score from baseline to Week 10 is -5.35 ,
	and the standard deviation (calculated from the standard error of the
	difference between the 2 mg and placebo groups and the number of
	subjects at baseline) is 15.06 on the basis of the results of Trial 331-
	12-283. By setting the number of subjects in the 2 mg group, 1 mg
	group, and placebo group as 148, 111, and 148, respectively
	(randomization ratio of 4:3:4), the power of detection is 86.1% for
	the comparison between the 2 mg group and the placebo group and is
	80.5% for the comparison between the 1 mg group and the placebo
	group in a test with a significance level of 5% (two sided).
	On the basis of the above considerations, the number of subjects will
	be set at 148 in the 2 mg group, 111 in the 1 mg group, and 148 in
	the placebo group (randomization ratio of 4:3:4).
Trial duration:	August 2018 to June 2023 (planned)
	The duration of participation in the trial by each subject will be up to
	20 weeks.

Table of Contents

Proto	col Synopsis	2
Table	of Contents	7
List o	f In-text Tables	13
List o	f In-text Figures	14
List o	f Appendices	15
List o	f Abbreviations and Definitions of Terms	16
1	Introduction	18
1.1	Background	18
1.2	Nonclinical Data	20
1.3	Clinical Data	21
1.3.1		
		21
1.3.1.1		21
1.3.1.2		23
1.3.1.3		25
1.4	Known and Potential Risks and Benefits	
2	Trial Rationale and Objectives	27
2.1	Trial Rationale	27
2.2	Rationale for CYP2D6 Genetic Testing and DNA Storage	
2.3	Rationale of Sample Storage for Biomarker Exploration	29
2.4	Trial Objectives	
3	Trial Design	
3.1	Type/Design of Trial	
3.2	Trial Treatments	32
3.2.1	Dosing and Regimen	32
3.2.2	Rationale for Dosing and Regimen	32
3.2.3	Rationale for Duration of Treatment	34
3.3	Trial Population	34
3.3.1	Number of Subjects and Trial Population	34
3.3.2	Subject Number Assignment	34
3.4	Eligibility Criteria	35

3.4.1	Informed Consent	35
3.4.2	Inclusion Criteria	36
3.4.3	Exclusion Criteria	38
3.5	Requirements for Caregivers	41
3.6	Endpoints	42
3.6.1	Primary Endpoint	42
3.6.2	Secondary Endpoints	42
3.6.3	Exploratory Endpoints	42
3.6.4	Safety Endpoints	42
3.6.5	Pharmacokinetic Endpoint	43
3.6.6	Pharmacogenomic Endpoint	43
3.6.7	Other Endpoints	43
3.7	Measures to Minimize/Avoid Bias	43
3.8	Trial Procedures	45

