3.2.2 Rationale for Dosing and Regimen

Doses and regimen were determined on the basis of the results of the 2 overseas trials (Trial 331-12-283 and Trial 331-12-284), as no significant differences due to ethnicity have been observed in the PK of brexpiprazole.

In Trial 331-12-283, the brexpiprazole 2 mg group showed a statistically significant improvement in change from baseline in CMAI total score compared with the placebo group. In patients with aggression in the baseline evaluation in Trial 331-12-283, improvement in the 2 mg group was greater than that in the placebo group.

These findings suggested that 2 mg might be the optimal dose in Japanese patients. Therefore, 2 mg was selected to verify superiority over the placebo group.

On the other hand, although the 1 mg group in Trial 331-12-283 did not demonstrate improvement greater than that in the placebo group among either the overall population or patients with aggression, in Trial 331-12-284, which was conducted using flexible doses, the 0.5 to 2 mg group showed greater efficacy than the placebo group among patients with aggression, raising the possibility that doses lower than 2 mg might be effective. On the basis of these findings, a 1 mg group was included so that information on the dose-response relationships in Japanese patients could be obtained and superiority over the placebo group can be confirmed if the 1 mg group demonstrates efficacy similar to that in the 2 mg group.

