6.4 Primary and Secondary Endpoint Analyses

6.4.1 Primary Endpoint Analyses

The primary endpoint will be change in CMAI total score from baseline to Week 10. The primary analysis will be conducted on the FAS by using MMRM analysis on the basis of the OC data set. For the analysis model, the treatment group (brexpiprazole 1 mg group, brexpiprazole 2 mg group, or placebo group), time point (Weeks 2, 4, 6, 8, or 10), medical care category (hospitalized or outpatient), prior use of antipsychotics (yes or no), and interaction between treatment group and time point will be included as factors, the baseline and interaction between the baseline and time point will be included as covariates, and the error variance and covariance structure will be unstructured. The Kenward–Roger method will be used to determine the degrees of freedom.

Between-group comparison will be performed by calculating the difference of the least squares mean between each of the brexpiprazole groups and the placebo group at Week 10. The fixed sequence procedure will be used to adjust the multiplicity of testing due to the performance of two comparisons (ie, the brexpiprazole 1 mg group versus the placebo group and the brexpiprazole 2 mg group versus the placebo group) to control the overall type I error rate. Initially, the brexpiprazole 2 mg group will be compared with the placebo group. Only if the difference is statistically significant at a significance level of 5% (two sided), the brexpiprazole 1 mg group will be compared with the placebo group at a significance level of 5% (two sided).

The least squares mean for each treatment group and the difference of the least squares mean between each brexpiprazole group and the placebo group, as well as their two-sided 95% CIs, will be calculated at each time point.

If any problems in convergence status arise in the estimation of variance components of MMRM, heterogeneous Toeplitz, heterogeneous autoregressive of order 1, and heterogeneous compound symmetry, which are error variance-covariance structures, will be applied in this order, and the first structure that achieves convergence will be used in the primary analysis. If anything other than an unstructured variance-covariance structure is selected, a sandwich estimator for standard errors will be used.

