3.5.10 Mini-Mental State Examination (MMSE)

The MMSE total score will be the sum of scores for MMSE Items 1 through 30.

4 Sample Size

In Trial 331-12-283, which was performed outside Japan, the 2 mg fixed-dose group showed superiority over the placebo group in patients with aggression (patients with aggressive behavior at baseline), thus suggesting that it may also be the optimum dose for Japanese patients. Efficacy was not observed in the 1 mg fixed-dose group, but in Trial 331-12-284, the efficacy of a dose less than 2 mg was suggested by the results obtained in patients from the flexible-dose (0.5 to 2 mg) group, who had aggression.

In this trial, a power of detection $\geq 80\%$ will be achieved for comparison between the placebo group and the 1 mg group to allow evaluation of superiority over the placebo group if equivalent efficacy is demonstrated in the 1 and 2 mg groups. For comparison between the 2 mg group (possible optimum dose) and the placebo group, a more sufficient power of detection will be obtained by changing the randomization ratio. In this trial, it is assumed that the difference between the 2 mg group and the placebo group in the change in the CMAI total score from baseline to Week 10 is -5.35, and the standard deviation (calculated from the standard error of the difference between the 2 mg and placebo groups and the number of subjects at baseline) is 15.06 on the basis of the results of Trial 331-12-283. By setting the number of subjects in the 2 mg group, 1 mg group, and placebo group as 148, 111, and 148, respectively (randomization ratio of 4:3:4), the power of detection is 86.1% for the comparison between the 2 mg group and the placebo group and is 80.5% for the comparison between the 1 mg group and the placebo group in a test with a significance level of 5% (two sided).

On the basis of the above considerations, the number of subjects will be set at 148 in the 2 mg group, 111 in the 1 mg group, and 148 in the placebo group (randomization ratio of 4:3:4).

5 Statistical Analysis Datasets

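### The 80.5% power stated for 1 mg versus placebo ignores the fixed sequence; the power to declare 1 mg superior is about 73% if both doses have the assumed effect

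*Protocol*

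**What the plan says.** Protocol 6.1 assumes, for 2 mg versus placebo, that the "change in the CMAI total score from baseline to Week 10 is -5.35", with a standard deviation of 15.06 and 148, 111 and 148 subjects on 2 mg, 1 mg and placebo. It gives 86.1% power for 2 mg and says the power "is 80.5% for the comparison between the 1 mg group and the placebo group". Both figures are for a two-sided test at the 5% level. The aim is set out just before: power of at least 80% "will be achieved for comparison between the placebo group and the 1 mg group to allow evaluation of superiority over the placebo group", should the two doses prove equally effective. The Synopsis and SAP Section 4 repeat this (Synopsis: "80.5% for the comparison between the 1 mg group and the placebo").

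The testing rule is in Protocol 6.4.1, with the same rule in SAP 8.1.1 and the Synopsis. The 2 mg dose is tested first. "Only if the difference is statistically significant at a significance level of 5% (two sided), the brexpiprazole 1 mg group will be compared". That second test is likewise against placebo at 5% two-sided.

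Protocol 3.2.2 gives two reasons for the 1 mg arm: dose-response information, and that "superiority over the placebo group can be confirmed if the 1 mg group demonstrates efficacy similar to that in the 2 mg group".

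**The concern.** Under a fixed sequence, 1 mg can be declared superior only if both tests are significant. The chance of that cannot exceed the power of either test alone, and it is lower than both unless one success guarantees the other. A power figure tied to the goal of evaluating superiority of 1 mg should therefore either include the first step or say that it does not. The sample-size texts do neither.

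Two things are at stake. The first is whether the plan meets its 80% target for the 1 mg claim. The second is how a 1 mg result that is not confirmed will be read. A reader of Protocol 6.1 would put the risk of failing to confirm an equally effective 1 mg dose at about 20%. If part of that risk comes from the 2 mg test and not from the 1 mg data, the reader should know.

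**Working it through.** **Inputs.** From Protocol 6.1: difference -5.35 (printed for 2 mg), SD 15.06, n = 148 (2 mg), 111 (1 mg), 148 (placebo), two-sided 5%. For 1 mg the documents print no difference; -5.35 is used because the text speaks of equal efficacy. The first step supports this choice.

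**1. Reproduce the printed figures (two-sample t test).** Standard error = SD × √(1/n_active + 1/n_placebo).

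- 2 mg: 15.06 × √(1/148 + 1/148) = 1.751; noncentrality 5.35/1.751 = 3.056; power 86.13%.
- 1 mg: 15.06 × √(1/111 + 1/148) = 1.891; noncentrality 5.35/1.891 = 2.829; power 80.47%.

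Both match the plan (86.1%, 80.5%). So the printed 80.5% is the power of the 1 mg test alone, with -5.35 in both dose groups.

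**2. Correlation of the two tests.** They share the placebo arm, so

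ρ = (15.06²/148) / (1.751 × 1.891) = 1.532 / 3.311 = 0.463.

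Multiplying the two powers as if independent (0.861 × 0.805 = 0.693) would understate the joint power.

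**3. Power under the sequence (bivariate normal, critical value 1.960).**

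P(both significant) = Φ₂(3.056 − 1.960, 2.829 − 1.960; ρ = 0.463) = Φ₂(1.096, 0.869; 0.463) = 0.732.

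**4. Power of the 1 mg test given that 2 mg is significant.** The normal-approximation power for 2 mg is 0.863, so 0.732/0.863 = 0.847.

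**5. Simulation check.**

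| Method | P(both significant) |
|---|---|
| Bivariate normal | 73.2% |
| Simulated, variance pooled over three arms | 72.9% |
| Simulated, separate two-arm t tests | 72.8% |

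The shortfall from 80.5% is 7.3 to 7.7 points. In 7.6% of simulated trials (pooled variance) the 1 mg comparison would have been significant but is never made because 2 mg failed.

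**6. If 1 mg is somewhat weaker.** These 1 mg effects are assumptions, not in the documents; 2 mg is held at -5.35 (normal approximation).

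| 1 mg difference | 1 mg test alone | Under the sequence |
|---|---|---|
| -5.0 | 75.3% | 68.8% |
| -4.5 | 66.3% | 61.3% |

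**The case against.** The strongest reply is that the printed figure is true as worded. It is given for one comparison in one test at 5%, reporting power per comparison is common, and no text says that 80.5% is the probability of declaring 1 mg superior at the end of the sequence. The sequence is not hidden either: in the Synopsis it appears directly before the sample-size rationale. All of this stands, and it is why the figure is not an arithmetic error. It does not settle the matter, because the figure supports a sentence promising at least 80% power for evaluating superiority of 1 mg, and in this plan that superiority can be concluded only through the first test.

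The promise could also be read as conditional on 2 mg having shown its effect. On that reading at least 80% is achieved, since the conditional power is about 85%. But 80.5% is not that number, so the text does not carry this meaning consistently.

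It is also fair to say that the dose-response purpose of the 1 mg arm is untouched: estimates and confidence intervals for both doses are produced whatever the tests show. That limits the consequence to the second purpose in Protocol 3.2.2, confirming superiority of 1 mg. Finally, -5.35 for 1 mg is inferred, though 80.5% is reproduced with it, and the weaker-effect rows are illustrations only.

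**Conclusion.** The concern holds. In the plan's own equal-efficacy scenario, the power to declare 1 mg superior is about 73% (72.8% to 73.2% by method), against a printed 80.5% and a target of at least 80%. The risk of not confirming an equally effective 1 mg dose is about 27% instead of about 20%.

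This rests on -5.35 in both dose groups, SD 15.06, the planned group sizes with no allowance for dropout (the sample-size text states none), and two-sample tests, which reproduce the plan's own figures. The power for 2 mg, type I error control and the planned analysis are sound on this point. The defect is a stated power that the gated design does not have, and it should be corrected.

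**What to change.** Change the wording in Protocol 6.1, the Synopsis and SAP Section 4:

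1. Label 86.1% and 80.5% as the power of each comparison taken alone.
2. Qualify the sentence promising at least 80% so that it refers to the 1 mg comparison taken alone.
3. Add a sentence such as: *Because 1 mg is tested only if 2 mg is significant, the power to conclude superiority of 1 mg is about 73% if the difference from placebo is -5.35 in both dose groups, and about 85% given that 2 mg is significant.*

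The cost is three text edits and a less favourable stated power for 1 mg. Sample size, test order and analysis stay as they are. For scale only: at 4:3:4 allocation with the same inputs, 80% power under the sequence would need about 172/129/172 subjects, 473 in total (80.6%, normal approximation), which is 66 more than the planned 407. That increase is not proposed here.
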